5.5.7. Immunogenicity Analysis

Details of immunogenicity analyses conducted in this study are presented in Sections 6.10 for Covid-19 and in Section 6.11 for Influenza.

5.5.8. Covid-19 Impact Analyses

In order to assess the impact of the Covid-19 pandemic on the ongoing study, the following additional outputs will be presented: the frequency of major PDs related to the pandemic and study drug compliance pre- and post-pandemic.

- (i) A table of frequencies for major PDs related to the Covid-19 pandemic. This can be identified in SDTM.DV dataset by DVTERM which includes the prefix "Covid-19-related" and DVSCAT= "Major".
- (ii) A listing of major PDs related to the Covid-19 pandemic will be presented.
- (iii) A table for Total Compliance for the periods pre-Covid-19 and post-Covid-19 will be presented, where pre/post-Covid-19 is defined as pre/post-January 1, 2020. Interruptions spanning across these two periods will be assigned to the pre-Covid-19 period.
- (iv) The number of events of Covid-19 related discontinuations will be presented.

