3.6.2 Study drug interruption

Study drug interruption should be avoided.

If study drug intake is interrupted by the patient for any reason, she/he must immediately inform the primary investigator / treating neurologist.

Study drug may be temporarily interrupted in response to an AE, a diagnostic or therapeutic procedure, a laboratory abnormality, a planned pregnancy, or for administrative reasons. The permitted maximum duration of the study drug interruption is 81 weeks for planned pregnancies and 12 weeks for other reasons (if exceeded, the patient will then be prematurely discontinued from the study).

In the event of a re-initiation of study drug, one tablet of ponesimod 2, 3, 4, 5, 6, 7, 8, 9, or 10 mg will be taken orally o.d. during the uptitration period (Day 1 to 14). During the maintenance period, patients will continue to take one tablet of ponesimod 20 mg orally o.d. [Table 6]. If a blister kit with the starting dose of 2 mg is not available at the site, re-initiation should be delayed until it becomes available (temporary treatment interruption).

Detailed guidance on how to re-initiate study drug in the event of drug interruption is provided in Appendix 5.

EudraCT 2009-011470-15 EDMS-ERI-206617631

Ponesimod / ACT-128800 / JNJ-67896153 Multiple Sclerosis Protocol AC-058B202 Version 12 15 March 2022, page 68/179

Confidential

Treatment period	Duration	Dose regimen
Titration	Day 1 and 2	2 mg
Titration	Day 3 and 4	3 mg
Titration	Day 5 and 6	4 mg
Titration	Day 7	5 mg
Titration	Day 8	6 mg
Titration	Day 9	7 mg
Titration	Day 10	8 mg
Titration	Day 11	9 mg
Titration	Day 12 to 14*	10 mg
Maintenance	Day 15 until EOT3	20 mg

Table 6:2-week gradual uptitration regimen

* An additional visit 14 days (± 1 day) after the day of re initiation (Re initiation Day 15) is mandated for patients with cardiovascular risk factors [see Appendix 5], but may be scheduled for any patient at the discretion of the investigator / treating neurologist. The titration kit will therefore include 3 additional tablets (to be used if applicable) for treatment on Day 15 17 (i.e., dose regimen 20 mg).

EOT3 End of Treatment

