3. SAMPLE SIZE DETERMINATION

As described in the Section 1.2.2, the sample sizes in the various phases of the study are determined by the treatment pathways starting with the core study.

POPULATIONS (ANALYSIS SETS) FOR ANALYSIS 4.

Table 1: **Description of Analysis Sets**

Analysis Sets	Description
All Randomized Set (RND)	The randomized analysis set includes all participants who were randomized in the core study.
Ponesimod Analysis Set (PAS)	This set includes all subjects who received at least one dose of ponesimod at any time during the core and/or the extension study.
Echocardiography Analysis Set (ECHO)	This includes all subjects in the PAS who have at least one echocardiography assessment after first dose of ponesimod.
Optical Coherence Tomography Analysis Set (OCT)	This includes all subjects in the PAS who have at least one OCT assessment after first dose of ponesimod.

An overview of the different analysis sets and their usage is given in Table 2 below.

Usage of Analysis Sets Table 2:

Analyses/Data Displays	RND	PAS	ECHO	OCT
Disposition	✓	✓		
Demographic characteristics		~		
Baseline characteristics		~		
Medical history		~		
Previous and concomitant medications		 ✓ 		
Protocol deviations		√*		
Treatment exposure		~		
Efficacy: Relapse		~		
Efficacy: MRI		~		
Efficacy: Neurological		~		
Efficacy: Ophthalmological				 ✓
Safety: Holter ECG		✓		

Safety: Echocardiography		\checkmark	
Safety: All other endpoints	~		
All subject listings	~		

*Subset on subjects entering the extension study.

ECG = electrocardiogram; ECHO = Echocardiography analysis set; OCT = Optical coherence tomography analysis set; PAS = Ponesimod analysis set; RND = All-randomized analysis set.

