5.4.1. Exposure and Compliance

5.4.1.1. Exposure to study treatment

All ponesimod drug administration data is taken from the study drug log and stored in SDTM.EC. ECSTDTC where EC.ECCAT = 'STUDY DRUG INTAKE'. The two EC datasets are concatenated for the purposes of this analysis.

Ponesimod exposure (years) for any given exposure period is derived as:

-[(Treatment end date - ponesimod start date + 1 day) - (End date of pregnancy interruption - Start date of pregnancy interruption + 1 day)] / 365.25, for subjects with planned pregnancy interruption and restart of the treatment,

- (Treatment end date - ponesimod start date + 1 day) / 365.25, regardless of interruptions, for all other subjects.

Duration of planned pregnancy study drug interruption (days) is defined as: min (EOS date, end date of pregnancy interruption) – Start date of pregnancy interruption + 1 day
In case of multiple planned pregnancies, all intervals between start date and end date of each pregnancy interruption will be subtracted from exposure.

Duration of planned pregnancy is excluded from all definitions of exposure duration and compliance with study treatment.

The following variables are derived for ponesimod exposure:

	1	
Exposure period	Start date	End date
Ponesimod exposure	First administration of	Last administration of ponesimod in the
during the core study	ponesimod in the core study	core study
(years)		
Ponesimod exposure	First administration of	Last administration of ponesimod in TP1
during TP1 (years)	ponesimod TP1	_
Ponesimod exposure	First administration of	Last administration of ponesimod in TP2
during TP2 (years)	ponesimod TP2	_
Ponesimod exposure	First administration of	Last administration of ponesimod in TP3
during TP3 (years)	ponesimod TP3	
Ponesimod exposure	First administration of	Max of [last administration of ponesimod
during AP3 (years)	ponesimod (in core or TP1)	in the core study, last administration of
		ponesimod in TP1, last administration of
		ponesimod in TP2, last administration of
		ponesimod in TP31

Table 10: Ponesimod exposure variables

AP = Analysis Period; TP = Treatment Period.

If end date is missing on last record in EC (e.g., if a subject is lost to follow-up), then date of last administration is taken as DS.DSSDTC when DSSCAT = 'Study termination'.

For each of the variables defined in Table 10 above, the following corresponding exposure variables are derived:

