5.4.1.2. Compliance with study treatment

Data on capsules/tablets dispensed/returned are not collected on the CRF, and so compliance cannot be assessed in this way. As a proxy, compliance is assessed as a percentage, calculated as:

(Cumulative exposure over defined exposure period with interruptions excluded / Cumulative exposure over defined exposure period with interruptions included) *100.

Corresponding categorical variables are derived for compliance in the categories: $< 80\%, \ge 80 - < 90\%, \ge 90 - < 95\%, \ge 95 - <= 100\%, =100\%$.

Compliance with study treatment is derived as:

- [duration of exposure with all interruptions excluded / duration of exposure with interruptions included (except interruption for planned pregnancy)] \times 100.

All other exposure and compliance variables will be defined in the same way, i.e., excluding the planned pregnancy interruption periods. In addition, the planned pregnancy interruptions will not be counted/considered an interruption for the variables: number of subjects with at least an interruption, number of treatment interruptions (> 3 days) or cumulative duration of interruptions.

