5.4.2. Analysis of Exposure

5.4.2.1. Exposure and compliance

Separate exposure tables are created for the AP3 exposure period as defined in Table 10 in Section 5.4.1.1 and for the corresponding compliance variables defined in Section 5.4.1.2 to present:

- Ponesimod exposure (years): descriptive statistics;
- Overall subject years exposure (sum over all subjects' exposure);

```
CONFIDENTIAL – FOIA Exemptions Apply in U.S.
```

- Ponesimod exposure by category (cumulative) (years): frequency counts and percentages;
- Ponesimod exposure with interruptions excluded (years): descriptive statistics;
- Ponesimod exposure by category with **interruptions excluded** (cumulative) **(years):** frequency counts and percentages;
- Number of treatment interruptions > 3 days: frequency counts and percentages;
- Number of subjects with at least 1 treatment interruption > 3 days: frequency counts and percentages;
- Cumulative duration (days) of interruptions > 3 days: descriptive statistics;
- Compliance (%): descriptive statistics (AP3 only);
- Compliance by category (%): frequency counts and percentages (AP3 only).

Corresponding listings of all exposure and compliance variables as defined in Sections 5.4.1.1 and 5.4.1.2 are provided separately for each defined exposure period.

All outputs for ponesimod exposure are based on the PAS.

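### SAP 5.5.8 charges interruptions that cross 1 January 2020 wholly to the pre-Covid period and compares unlike patient groups, so its compliance table could mask a modest decline

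*SAP*

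**What the plan says.** The stated aim of SAP Section 5.5.8 is to assess how the pandemic affected the study. Its item (iii) is the only one of four outputs that measures compliance: "A table for Total Compliance for the periods pre-Covid-19 and post-Covid-19 will be presented". The cut is given as "pre/post-Covid-19 is defined as pre/post-January 1, 2020", and the rule for interruptions lying across it is "Interruptions spanning across these two periods will be assigned to the pre-Covid-19 period".

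Section 5.4.1.2 defines compliance as "Cumulative exposure over defined exposure period with interruptions excluded / Cumulative exposure over defined exposure period with interruptions included) *100". Table 10 in Section 5.4.1.1 lists the exposure periods to which this applies (core study, each extension treatment period, and Analysis Period 3). It defines none that starts or ends at 1 January 2020.

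Section 5.5.8 names no analysis set and does not limit the table to patients seen on both sides of the cut. The general statement is in Section 5.4.2.1: "All outputs for ponesimod exposure are based on the PAS". Table 1 in Section 4 defines that set: "This set includes all subjects who received at least one dose of ponesimod at any time during the core and/or the extension study".

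Two provisions limit how long a relevant interruption can be. Protocol Section 3.6.2 says "The permitted maximum duration of the study drug interruption is 81 weeks for planned pregnancies and 12 weeks for other reasons", and SAP Section 5.4.1.1 says "Duration of planned pregnancy is excluded from all definitions of exposure duration and compliance with study treatment". Only the 12-week limit therefore matters for this table.

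**The concern.** Two features work against a before-and-after reading.

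First, the crossing rule moves days in one direction only. A patient off drug from December 2019 into 2020 has all missed days counted as pre-Covid, including those in 2020. Nothing in the text moves days the other way. Because no pre- or post-Covid exposure period is defined, the missed days and the exposure time that contains them may also end up in different columns.

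Second, the two columns need not hold the same patients. The cohort is closed: the protocol synopsis puts the last patient's first visit in Q2 2011, and the rationale for Global Amendment 11 says nobody new will start treatment. Every patient ever dosed can contribute to the pre column, but only those still on drug in 2020 can contribute to the post column. No within-patient comparison is planned.

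At stake is whether the table can do its stated job. Protocol Appendix 10 allows temporary interruption of up to 12 weeks where pandemic conditions prevent follow-up or adequate safety monitoring, so compliance is where part of any pandemic effect would appear.

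**Working it through.** The documents give no figure for this table, no compliance data, no interruption frequency and no count of patients on drug at 1 January 2020. There is nothing to reproduce, and the ranges below are assumptions unless a source is named.

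**1. How many days can move.** The limit is 12 weeks, or 84 days (Protocol 3.6.2). The latest crossing interruption has its first missed day on 31 December 2019 and its last on 23 March 2020. It leaves 31 + 29 + 23 = 83 days after the cut, the most that can move per patient within the limit.

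**2. One patient, to show the direction.** Assume 9 years before the cut (3,287.25 days), 3 years after (1,095.75 days), and an 84-day interruption split 42/42.
- Calendar-day split: pre 1 − 42/3,287.25 = 98.7%; post 1 − 42/1,095.75 = 96.2%.
- SAP rule: pre 1 − 84/3,287.25 = 97.4%; post 100%.

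**3. The group mean, which is what the table shows.** Rise in mean post compliance = (share of patients crossing) × (days moved) / (post-cut exposure days). As a rough guide to the share, 0.1 to 0.5 interruptions a year lasting 7 to 42 days gives 0.1 × 7/365.25 = 0.2% up to 0.5 × 42/365.25 = 5.8%. The table uses 0.5% and 5%; entries are percentage points.

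| Post-cut exposure | Share crossing | 42 days moved | 83 days moved |
|---|---|---|---|
| 3 years | 0.5% | 0.02 | 0.04 |
| 3 years | 5% | 0.19 | 0.38 |
| 1 year | 0.5% | 0.06 | 0.11 |
| 1 year | 5% | 0.57 | 1.14 |

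The pre figure for the same patients falls by less, because their pre-cut exposure is longer: at most 0.05 × 83/3,287.25 = 0.13 points with 9 pre-cut years.

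**4. Evidence of early leavers.** Protocol Section 1.3.2.4 reports, for the 20 mg group at the 31 March 2019 cut-off, a median exposure of 8.02 years and 817 subject-years in total. Group size is not given there. From Protocol 1.3.2.3, 464/4 = 116 randomized, less 2 untreated, gives 114. Adding a third of the placebo arm (116/3 ≈ 39) gives about 153. Mean exposure is then 817/114 = 7.2 years, or 817/152.7 = 5.4 years. Both lie below the median, which points to a tail of patients who left early and can appear only in the pre column.

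**5. What the patient mix could do.** Let s be the share of patients who stayed into 2020, a their pre-cut compliance, a − g that of leavers, and d the true fall among stayers. The pre column averages a − (1 − s)g and the post column a − d. The apparent change is (1 − s)g − d, so a true fall of up to (1 − s)g shows as no fall.
- s = 0.6, g = 1 point: 0.4 × 1 = 0.4 points masked.
- s = 0.4, g = 5 points: 0.6 × 5 = 3.0 points masked.
- g = 0: nothing masked.
- g below 0 (leavers more compliant): the table overstates a fall.

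**The case against.** The crossing rule can be defended as attribution by onset. An interruption that began in 2019 was not started by the pandemic, which could at most have prolonged it, and every interruption starting on or after 1 January 2020 still counts as post-Covid. Within the 12-week limit the last crossing interruption ends on 23 March 2020, 52 days before the 14 May 2020 amendment that introduced the pandemic guidance. This stands as a reason why the effect is small. It does not make the table coherent, because days off drug in 2020 remain uncounted in the column that covers 2020.

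Other outputs also bear on the pandemic: a table and a listing of Covid-related major deviations, and a count of Covid-related discontinuations. That also stands, although none of them measures compliance.

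A reader might infer more: that the table hides an adverse effect, that it will show a swing of several points, or that both features necessarily favour the later period. The documents support none of these. No compliance data exist in them from which to say a fall occurred. The swing belongs to a single patient and not to a group mean. The direction of the mix effect depends on leavers having been less compliant while on drug. Under Section 5.4.1.1 an interruption needs a restart and is counted only up to the last dose, so stopping for good does not by itself lower a leaver's compliance. That all treated patients enter the pre column is also an inference from Section 5.4.2.1; Section 5.5.8 does not say it.

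**Conclusion.** The point holds in a limited form. The crossing rule biases the comparison in one direction, towards better compliance after the cut. Its size in the post column is about 0.02 to 0.4 points for 0.5% to 5% of patients crossing with 3 post-cut years, and up to about 1.1 points with 1 year and 5% crossing.

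The difference in patient mix is potentially larger, masking a fall of 0.4 to 3.0 points if 40% to 60% of patients stayed and leavers were 1 to 5 points less compliant. It is conditional on that gap, which the documents do not establish, and it could be nil or reversed. The supported conclusion is that the table could mask a modest decline, not that it does. All objectives are exploratory and no efficacy or safety conclusion rests on this output, so this is a low-priority improvement.

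**What to change.** In SAP Section 5.5.8:
- Split each crossing interruption, and the exposure time, at 1 January 2020 by calendar day, so that numerator and denominator refer to the same period. State both exposure periods explicitly.
- Name the analysis set. Add pre and post compliance, with the within-patient change, for patients exposed in both periods. Keep the all-subject columns as background.

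The dates are already in the study drug log, so the cost is a few lines of text and a date split in the programming. The paired comparison will contain fewer patients than the present pre column and describes only those who stayed, which a footnote should say.

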5.5.9. Regional Crisis Impact Analyses

In order to assess the impact of the regional crisis in Ukraine and Russia on the ongoing study, the following additional output will be presented:

(i) A listing of all major PDs related to the regional crisis.

5.6. Interim Analyses

An iCSR SAP AC-058B202_SAP_V3_2307_EDMS-ERI-197686018_3.0 was prepared, describing the analyses and presentation of all safety, tolerability and selected efficacy endpoints, for the interim clinical study report (iCSR) (EDMS-ERI-181610698, 1.0) of the pooled AC-058B201 (core) and AC-058B202 (extension) studies, to support the ponesimod New Drug Application (NDA) / Marketing Authorization Application (MAA)

5.6.1. Data Monitoring Committee (DMC) or Other Review Board

A DMC convened for the ponesimod program was disbanded on 30th Sept. 2021.

6. SUPPORTING DOCUMENTATION

6.1. Appendix 1 List of Abbreviations

%pred FEV ₁	FEV ₁ expressed as % of predicted normal value
%pred FVC	FVC expressed as % of predicted normal value
ADaM	Analysis data model
AE	Adverse event
AESI	Adverse event of special interest
ALP	Alkaline phosphatase
ALT	Alanine aminotransferase
AP1	Analysis period 1
AP2	Analysis period 2
AP3	Analysis period 3
ARR	Annualized relapse rate
AST	Aspartate aminotransferase
ATC	Anatomic therapeutic chemical
BP	Blood pressure
bpm	Beats per minute
CDA	Confirmed disability accumulation
CDISC	Clinical Data Interchange Standards Consortium
CFR	(US) Code of Federal Regulations
CI	Confidence interval
CL	Confidence limit(s)
CRF	Case report form
CRO	Contract research organization
CSR	Clinical study report
CUAL	Cumulative unique active lesions
DBP	Diastolic blood pressure
DMTs	Disease modifying therapies for MS
ECG	Electrocardiograph
EDSS	Expanded Disability Status Scale
ELISA	Enzyme-linked immunosorbent assay
EMA	European Medicines Agency
EOS	End-of-study

EOT	End-of-treatment
FAS	Full analysis set
FDA	(US) Food and Drug Administration
FEV_1	Forced expiratory volume in 1 second
FS	Functional system
FU	Follow-up
FVC	Forced vital capacity
GCP	Good Clinical Practice
Gd+	Gadolinium enhancing
ICF	Informed Consent Form
ICH	International Conference on Harmonisation
IDMC	Independent Data Monitoring Committee
KM	Kaplan-Meier
MedDRA	Medical Dictionary for Regulatory Activities
MRI	Magnetic resonance imaging
MS	Multiple Sclerosis
OCT	Optical coherence tomography
PAS	Ponesimod analysis set
PD	Pharmacodynamic
РК	Pharmacokinetic
PPS	Per-protocol analysis set
РТ	Preferred term
QT_{C}	Corrected QT interval
QT_CB	QT interval corrected for heart rate using Bazett's formula
$QT_{C}F$	QT interval corrected for heart rate using Fridericia's formula
RMS	Relapsing multiple sclerosis
RNFL	Retinal nerve fiber layer
RRMS	Relapsing-remitting multiple sclerosis
SAE	Serious adverse event
SAF	Safety analysis set
SAP	Statistical Analysis Plan
SAS	Statistical analysis system
SBP	Systolic blood pressure

CONFIDENTIAL – FOIA Exemptions Apply in U.S.

Status: Approved, Date: 20 September 2023

SBP	Systolic blood pressure
SCR	Screened analysis set
SD	Standard deviation
SDTM	Study Data Tabulation Model
SE	Standard error
SI	Standard International
SOC	System organ class
SOP	Standard operating procedure
SPMS	Secondary progressive multiple sclerosis with superimposed relapses
TBIL	Total bilirubin
TEAE	Treatment-emergent adverse event
TP1	Treatment Period 1
TP2	Treatment Period 2
TP3	Treatment Period 3
ULN	Upper limit of the normal range
WHO	World Health Organization
WHODRUG	WHO drug dictionary

6.2. Appendix 2 Changes or Clarifications to Protocol-Planned Analyses

Protocol	Change	Rationale
section		
5.2	It is stated that "Baseline is defined as the last assessment performed prior to the first administration of study treatment in AC-058B201 for the analyses comparing treatment groups as randomized in AC-058B201 including the placebo treatment period", however, no analyses including the placebo period are performed as part of this SAP. The following populations are	An analysis by treatment groups as randomized in AC-058B201 would analyze subjects who have been receiving ponesimod for 8+ years as placebo, although they received placebo only for the first 6 months. Therefore, the placebo period is excluded. It is also considered important from a safety perspective that baseline is defined immediately prior to the initiation of ponesimod. These populations were not deemed
5.2	 The following populations are defined: "Modified intent-to-treat set (mITT) – extension population": This analysis set includes all randomized patients who received at least once ponesimod dose in the combined studies AC-058B201 and AC-058B202 and had at least one post-baseline MRI examination. Per-protocol (MRI) – extension population "The Per-protocol (MRI) – extension population includes all patients of the Per-protocol (MRI) set for AC-058B201 who completed at least Visit E7 of AC-058B202 and did not have any major protocol violation in AC-058B202". These are not used for any analyses in this SAP. 	necessary as the objectives of the analysis are exploratory in nature.
5.3	It is stated that "The treatment groups will be analyzed as randomized in AC-058B201, by pooled dose groups and by treatment pathway across the combined core study and extension study and by individual treatment periods in the extension study." No analyses by treatment pathway or as randomized by AC-058B201	An analysis by treatment groups as randomized in AC-058B201 would analyze subjects who have been receiving ponesimod for 8+ years as placebo, although they received placebo only for the first 6 months. There are 8 different treatment pathways across the core and extension studies combined. This was not foreseen at the time of

